8. Requiring any of the following medications currently or within the past 4 weeks: psychotropics (including sedatives/hypnotics, antidepressants, neuroleptics), prescription analgesics (excluding those listed in inclusion criterion #2 above), anticonvulsants, antihypertensives, antiarrhythmics, antiretroviral, and cholesterol lowering medications. Nicotine replacement therapy (patch, inhaler, gum, or nasal spray) will be allowed for nicotine-dependent subjects.

Note: Use of a short-acting benzodiazepine (e.g., oxazepam) for insomnia during Days 8-14 will not disqualify a subject.

9. Current dependence (based on the M.I.N.I.) on any psychoactive substance (other than that listed in inclusion criterion #2, caffeine or nicotine) that requires detoxification.
10. Have donated blood within the last 8 weeks.
11. Have participated in an investigational drug study within the past 3 months.
12. Have such “poor” veins that even a single venipuncture cannot be obtained during screening.
13. Have active tuberculosis (positive tuberculin test and/or confirmatory diagnostic chest x-ray).
14. Have active syphilis.

**Notes on inclusion/exclusion criterion:** Potential subjects who are positive for syphilis (as detailed in [Section 15.5.4.2](#)) will not be eligible for study participation and will be referred for appropriate follow-up and/or treatment, if required.

The infectious disease panel for hepatitis is performed as an aid to determine if the prospective subject has been exposed to a hepatitis virus. Positive hepatitis results do not exclude a prospective subject from participation unless there is an indication of active liver disease.

Tuberculin test (purified protein derivative [PPD]) and/or a chest x-ray will be performed on all subjects. A positive PPD result does not exclude a prospective subject from participation, but if diagnostic tests (e.g., chest x-ray) indicate that active disease is present, subjects will be excluded from participation.

If any tests are positive, the subject will be notified of the test results and referred for treatment.

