#### **14.3.4 Days 8-14 (Open-Label, Continuation Treatment)**

Subjects who successfully meet the definition for “completer” based on Days 1-7 (i.e., receives at least one dose of study medication on Day 7 and completes the 3.5-hour post-dose SOWS-Gossop assessment on Day 7) and if clinically indicated (as determined by the Site Investigator) may continue to receive lofexidine to control symptoms for up to an additional 7 days during Days 8-14. Subjects may be treated as inpatients or outpatients, depending on the wishes of the investigator and the subject, using open-label, variable dose lofexidine (as determined by the Site Investigator, but not to exceed 3.2 mg/day). The rationale for the decision to continue treatment or not and the Site Investigator’s decision to continue treatment through either an inpatient or outpatient setting must be documented in the subject’s source document and eCRF. Lofexidine treatment will terminate and the subject will be discontinued from the study when the Site Investigator judges that the acute phase of opioid withdrawal is essentially complete and the subject no longer needs treatment for abstinence. In any event, no subject will continue to receive lofexidine treatment for more than 14 days total from the onset of abstinence. If being treated as an outpatient, the subject must return to the clinic daily for assessment (see a complete list of assessments in [Table 1](#) of [Section 15](#)).

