## 14.5 Study Discontinuation

### 14.5.1 Subject Discontinuation

A subject can withdraw his/her consent for participation in the study at any time without prejudice. The Site Investigator may discontinue a subject if s/he deems it clinically appropriate for any reason. Additionally, the Site Investigator must discontinue a subject for any of the following reasons:

1. Cardiovascular events (see [Section 14.5.2](#)).
2. Serious medical problem thought to be related or unrelated to the study medications.
3. Intercurrent illness or medical complications that, in the opinion of the site investigator, preclude safe administration of study medications.
4. Evidence of illicit drug use while participating in the study during Days 1-7.
5. Alcohol or other sedative/hypnotic withdrawal signs and symptoms developing following enrollment into the study.
6. Requiring therapy with an exclusionary drug.
7. Lack of compliance with protocol and/or unit procedures.
8. During Days 1-7, missing more than 2 doses of study medication in a single 24-hour period or missing more than 6 doses of study medication prior to meeting “completer” criteria (i.e., receives at least one dose of study medication on Day 7 and completes the 3.5-hour post-dose SOWS-Gossop assessment on Day 7).

At any time after a subject meets “completer” criteria, they may be discontinued by the Investigator if s/he feels that the subject has achieved the treatment goal of acute detoxification/ transition. This judgment by the Site Investigator will be made and recorded daily in the subject’s source document and on the eCRF on Days 7 (after end of double-blind dosing but before initiating open label dosing) through 14.

Subjects who are removed from study treatment because of adverse events (AEs) or serious adverse (SAEs) will be followed until they are medically stabilized to the satisfaction of the attending physician (see [Sections 15.5.1](#), [16.7](#), and [16.8](#)). Appropriate safety evaluations will continue to be collected until the subject is discharged from the treatment center or the maximum 14-day treatment period has expired. This stabilization can include medically supervised opioid withdrawal (involving behavioral therapy, rescue opioid medications, and/or non-opioid pharmacotherapy) or referral to an appropriate methadone or buprenorphine therapy program.

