## 14.6 Concomitant Therapy

If the subject is admitted to the inpatient study unit the day before Baseline (i.e., Day -1), a single dose of a short-acting opioid (e.g., morphine) may be administered if needed to keep the subject reasonably comfortable; however, the administration may not occur after 8 PM on Day -1.

The concomitant medications or therapies listed below are permitted during Days 1-7 and Days 8-14 of the study.

1. Multivitamins ( $\leq 1$  tablet orally, administered daily at 9 AM).
2. Guaifenesin (for cough) ( $\leq 2$  teaspoons orally every 2 hours, as needed [PRN]).
3. Alumina, Magnesia, and Simethicone (for emesis and nausea) ( $\leq 30$  mL orally every 4 hours, PRN).
4. Dioctyl sodium sulfosuccinate (for constipation) ( $\leq 100$  mg orally every 8 hours, PRN).
5. Psyllium hydrocolloid suspension (for constipation) ( $\leq 1$  tablespoon orally every 12 hours, PRN).
6. Bismuth sulfate (Pepto-Bismol®) (for diarrhea) ( $\leq 6$  doses of 30 mL orally every 24 hours, PRN).
7. Acetaminophen (for headache, muscle aches, or other discomfort) ( $\leq 4$  doses of  $\leq 650$  mg orally every 24 hours).
8. Zolpidem (for insomnia) ( $\leq 10$  mg orally, PRN, may repeat 1 time if administered before 5:00 AM (i.e., 3 hours before the first morning dose of lofexidine or placebo). Zolpidem must not be administered before 11:00 PM (which is the time of the last daily dose of lofexidine or placebo).
  - 8a. Note: A short-acting benzodiazepine (e.g., oxazepam) may be used ad libitum for insomnia during the second part of the study (i.e., Days 8-14).
9. Nicotine replacement therapy (patch, inhaler, gum, nasal spray).

All other medications must be approved by the Sponsor's Medical Monitor before administration. If a subject requires any other medication for intolerable nausea and emesis (including a prescription opioid or non-opioid or an over-the-counter opioid or non-opioid) other than alumina, magnesia and simethicone, the subject will be discontinued from the study and given appropriate treatment according to the standard of care (see [Section 14.5.1](#)).

All medications taken will be recorded in the subject's source document and eCRF along with dose, dates of administration, and reason for use.

Psychosocial therapy (e.g., art, music, group sessions) will be allowed per standard of care at individual study sites. Acupuncture, however, will not be allowed. All therapies will be recorded in the subject's source document and eCRF.

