### 15.3.2 Days 8-14 (Open-Label, Continuation Treatment)

The assessments listed below will be performed daily (unless otherwise specified) on Days 8-14 (see [Section 15.3.3](#) for assessments/procedures required for discontinuation from the study).

- Efficacy assessments before dosing including:
  - SOWS-Gossop;
  - OOWS-Handelsman;
  - MCGI (Subject and Rater);
  - VAS-E; and
  - COWS.
- C-SSRS before dosing (Since Last Visit version; [Appendix 10](#)).
- Concomitant medication assessment.
- Completion of detoxification as assessed by the Site Investigator.
- Pill count to measure compliance with previous day’s doses.
- Resting (sitting or recumbent, if required, for treatment of an AE) and standing blood pressure and pulse at least once daily before dosing and 3.5 hours after dosing on Days 8-13 and once pre-dose Day 14. Note that if subjects are being treated on an outpatient basis and cannot stay in the clinic for measurement of the 3.5-hour post-dose vital signs required on Days 8-13, they will be given a portable digital blood pressure machine for measurement of their vital signs at this required time point. They will also be provided a diary ([Appendix 8](#)) to record the measurements.
- AE assessment.

- 12-lead ECGs (in duplicate) will be done before the first daily dose and 3.5 hours after the first daily dose on Day 8. On Day 14, 12-lead ECGs (in duplicate) will be done once before a dose on that day.
- Clinical laboratory tests as clinically warranted.
- Complete physical examination as clinically warranted.

Qualitative urine drug screening (by on-site use of “dipsticks”) will be done at least every other day to monitor for contraband (inpatient setting) or illicit (outpatient setting) drug use.

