#### 15.5.4.3 *Urine Toxicology Screening*

Qualitative urine drug screening (UDS) will be performed at screening for all subjects, at Baseline, and at least every other day for the following drugs: amphetamines/methamphetamines, cocaine, barbiturates, opiates, benzodiazepines, cannabinoids, methadone, and buprenorphine. The central lab will provide standard sets of UDS “dipsticks” for use across all sites.

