Only days when the patient was taking active treatment will be considered. Days after active administration will be disregarded.

For the calculation of the daily number of medications taken, the number of distinct coded drug names via the WHO dictionary will be used rather than verbatim terms.

Justification

To make the definitions within this analysis clearer.

Change 14

Section 6.13 Safety analysis

Add the text in bold

All subjects who receive at least dose one of study medication will be included in the analysis of safety.

Safety measures will be summarized for the following subject cohorts for the open label phase:

- \neq All treated subjects;
- ≠ Treated subjects without urinary evidence of illicit drug use (i.e. any positive result in the urine drug screen during the open-label phase, including all categories); and
- ≠ Treated subjects with urinary evidence of illicit drug use (may be further subdivided by type of illicit drug used).

Safety measures will only be summarized for all treated subjects for the double blind phase.

Extent of exposure

Extent of exposure will be described by whether the subject took the trial medication and the number of days exposure to double-blind study medication (last date of double-blind medication minus first date of double-blind medication + 1). Average daily dose of double-blind study

Effective: 24-Dec-2014

Page 13 of 29

medication will also be calculated **by number of doses/exposure (days)**. Exposure to open-label medication will also be calculated as last date of open-label medication – first date of open-label medication + 1. No allowance will be made for breaks in therapy in the exposure calculations. Average daily dose of open-label study medication will also be calculated. If the date of last dosing is completely missing for the trial medication then the date of last dosing will be taken for analysis purposes as the date the medication was last dispensed. As there are no open-label dosing dates recorded on the eCRF, dates of visits will be used instead. In particular it will be assumed that open-label dosing starts one day after double-blind dosing ceases.

Justification

To make the definitions clearer.

Change 15

Section 6.13 Safety analysis

Vital Signs During the Double-Blind Phase

The following text was amended:

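### Open-label safety cohorts: counting every positive urine screen as illicit drug use takes in the benzodiazepine that the protocol permits on Days 8-14

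*SAP*

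**What the plan says.** Protocol 17.3.2 and SAP 6.13 summarise open-label safety for all treated subjects and for two cohorts: those without and those with urinary evidence of illicit drug use. Neither section defines that evidence. SAP 6.13 summarises the double-blind phase for all treated subjects only.

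Addendum 1, Change 14, supplies the definition. It is printed on the first cohort's bullet, which describes subjects "without urinary evidence of illicit drug use (i.e. any positive result in the urine drug screen", and in full it is "any positive result in the urine drug screen during the open-label phase, including all categories". The bullet for the cohort with evidence carries no definition, only an option to subdivide by type of illicit drug. The stated reason for the change is clarity.

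The panel in Protocol 15.5.4.3 is "amphetamines/methamphetamines, cocaine, barbiturates, opiates, benzodiazepines, cannabinoids, methadone, and buprenorphine". Under Protocol 15.3.2, screening on Days 8-14 "will be done at least every other day to monitor for contraband (inpatient setting) or illicit (outpatient setting) drug use". Item 8a of the permitted list in Protocol 14.6 reads: "A short-acting benzodiazepine (e.g., oxazepam) may be used ad libitum for insomnia during the second part of the study".

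**The concern.** The two cohorts are there so that a reader can see open-label safety with and without illicit drug use. A rule that counts every category takes no account of why a screen is positive. On the days that define the cohorts, one panel category covers a drug that the protocol allows. A subject who follows the protocol can therefore be reported as an illicit drug user.

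The misplacement need not be neutral. Protocol 12.9 says that sedatives may enhance lofexidine's central sedative effects. Sedation in permitted benzodiazepine users would then appear under illicit use, and the other cohort would lose those subjects selectively.

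**Working it through.** The plan gives no figure to reproduce, so the check sets the passages side by side.

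1. **What is new.** The cohort bullets in SAP 6.13 and Protocol 17.3.2 have no parenthetical definition. Change 14 added it.
2. **What it defines.** The parenthetical directly follows the words for urinary evidence of illicit use, so the natural reading is that it explains that term. On this reading, one open-label positive in any category puts a subject in the cohort with evidence.
3. **Overlap with permitted drugs.** The list in Protocol 14.6 has 10 entries (items 1 to 9 plus 8a). Only item 8a names a panel category, benzodiazepines. Protocol 14.6 and 15.6.2 also allow other medication with the Medical Monitor's agreement, and such a drug could fall in a panel category too.
4. **Overlap in time.** Item 8a applies to Days 8-14, the period over which the cohorts are defined.
5. **Whether the cohort can fill.** Mandatory discontinuation for illicit drug use applies only to Days 1-7 (Protocol 14.5.1, item 4), so subjects with positive screens can remain in the open-label phase.
6. **The rule applied to three subjects:**

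| Open-label screens | Medication record | Cohort under Change 14 | Does the label fit? |
|---|---|---|---|
| No positive | Any | Without | Yes |
| Cocaine positive | No permitted or approved drug of that category | With | Yes |
| Benzodiazepine positive only | Short-acting benzodiazepine for insomnia, dated just before the screen | With | No |

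7. **Whether anything repairs the third row.** Subdivision by drug type is optional and works inside the cohort with evidence, so it moves nobody out. The changes listed in Addendum 2 amend Sections 6.2, 6.3, 6.9.1, 6.9.2 and 6.10, and leave 6.13 alone. The visible text of the SAP and both addenda contains no exemption.
8. **Size.** Let N be the number of open-label subjects, u the share taking the permitted drug, d the chance that at least one screen detects it, and o the chance of another positive that is truly illicit. The number mislabelled is N × u × d × (1 − o), with d and o taken among users. The documents give none of u, d or o. The result runs from zero (no use, or no detection) up to N × u (every user detected and none with another positive).

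**The case against.** The strongest case for leaving the rule alone is that it is objective and needs no judgement about medication records. It also keeps sedative-exposed subjects apart, which Protocol 12.9 gives some reason to want. Benzodiazepine positives can already be shown by drug type, concomitant medications are coded and tabulated, and SAP 6.1 allows further tables if the data warrant them. All of this is fair. It argues for keeping the all-category split, but not for calling it illicit use, and none of these provisions returns a permitted user to the other cohort.

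A reader might infer more than the documents support:

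- **That the cohorts are inverted.** Taken word for word, the parenthetical could describe subjects without evidence as those with positives. The natural reading is the one in step 2, and the cohorts are plainly complements. Its placement is a copy-editing matter.
- **That the note to exclusion criterion 8 settles cohort membership.** It says "Use of a short-acting benzodiazepine (e.g., oxazepam) for insomnia during Days 8-14 will not disqualify a subject". That concerns eligibility and says nothing about tabulation.
- **That frequent screening implies many mislabelled subjects.** Screening frequency does not measure misclassification when use, detection and timing are all unknown. Subjects may also leave before Day 14 (Protocol 14.3.4 and 14.5.1).
- **That the sponsor has no exemption anywhere.** Parts of both addenda cannot be seen, including the content under the tables heading in Addendum 2. A footnote there could carry one.
- **That item 8a is wrong because Protocol 12.9 lists sedatives among drugs not to be given with lofexidine.** The sponsor should reconcile those two sections, but this point takes no position on it.

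**Conclusion.** The definition is wrong as written, and the point is minor. It labels as illicit a positive that may reflect use the protocol allows. The conclusion assumes that the parenthetical defines evidence of illicit use and that no exemption stands in text that cannot be seen.

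Only the open-label safety summaries for the two cohorts are affected, and these are descriptive. The all-treated open-label summary, the double-blind safety summaries and the efficacy analyses do not use the split. The number of subjects affected cannot be computed and may be zero, so this is a finding about the definition and does not show that any result is distorted.

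**What to change.** Amend SAP 6.13 as follows.

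- Put the definition on the bullet for the cohort with evidence, and define the other cohort as its complement. The move itself is editorial.
- Do not count a positive as illicit when the concomitant-medication record documents a permitted or Medical Monitor-approved drug of that category within a look-back window before the screen. The SAP should state the window's length before unblinding. The documents give no detection time from which to derive it here.
- Use recorded dates only. SAP 6.2 replaces missing medication dates with worst-case dates, such as the end of the month for a stop date, which would widen the match and excuse more positives.
- Count every other positive as illicit, including those whose medication dates are missing.
- Keep the all-category split as a supplement, labelled as any positive screen, with documented-use positives shown separately.

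The cost is SAP wording, one dated merge and a supplementary set of tables. The data are already collected: Protocol 14.6 requires dose, dates and reason for each medication, and SAP 6.13 codes the drug names.

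There are three downsides. The rule depends on complete medication records, which for outpatients rest partly on self-report. A class-level dipstick cannot confirm which drug was taken, so some non-permitted use may be excused. Some sedative-exposed subjects will enter the cohort without illicit use. The supplement lets a reader see the effect of all three. No change to the permitted-medication rule is implied.

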## 10 INVESTIGATIONAL PLAN

### 10.1 Overall Design

This is a Phase 3, two-part, multicenter study to evaluate the dose-response, efficacy, and safety of lofexidine in alleviation of symptoms in subjects undergoing total and abrupt withdrawal from short-acting opioids. Any subject dependent on short-acting opioids (the primary projected indication for lofexidine) about to undergo opioid withdrawal will be eligible. Subjects will be evaluated for their compliance with protocol inclusion/exclusion criteria during a screening period, lasting up to 7 days.

The first part of the study will use an inpatient, randomized, double-blind, and placebo-controlled design (Days 1-7) followed by a second part, an open-label, continuation treatment (Days 8-14). A total of 600 subjects will be randomized to receive lofexidine 2.4 mg total daily dose (0.6 mg QID), lofexidine 3.2 mg total daily dose (0.8 mg QID), or matching placebo in a 3:3:2 ratio (225:225:150) for 7 days (i.e., during the most intense stage of

withdrawal). During the second part of the study (Days 8-14), all subjects, regardless of their treatment assignment (which will remain double-blinded), who successfully meet the definition for “completer” based on Days 1-7 (i.e., receives at least one dose of study medication on Day 7 and completes the 3.5-hour post-dose SOWS-Gossop assessment on Day 7), will be eligible to receive open-label, variable dose lofexidine treatment (as determined by the Site Investigator, but not to exceed 3.2 mg/day) for up to an additional 7 days in either an inpatient or outpatient setting depending on the wishes of the investigator and the subject. No subject will receive lofexidine for more than 14 days total from the onset of abstinence. There will be no initial dose run-up and no mandated terminal dose taper. Efficacy and safety assessments will be made daily (see detailed Schedule of Assessments in [Table 1 of Section 15](#)). Qualitative urine drug screening will be done every other day to monitor for contraband (inpatient setting) or illicit (outpatient setting) drug use.

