## 13 TREATMENT PLAN

### 13.1 Investigational Agents

On Day 1 of the Inpatient Treatment part of the study, subjects will be randomized to one of two dose levels of lofexidine or placebo and receive the following daily treatment regimens through Day 7: lofexidine 2.4 mg/day (administered as 3 x 0.2 mg tablets and 1 placebo tablet QID), lofexidine 3.2 mg/day (administered as 4 x 0.2 mg tablets QID), or matching placebo (administered as 4 x placebo tablets QID). In order to maintain the treatment blind, all subjects will receive a total of 16 tablets per day whether active, placebo, or in combination to achieve the assigned dose. Tablets will be provided in subject-specific kits, containing 7 blister cards (one for each study day). Each blister card will contain 4 rows of 4 tablets each, appropriately marked to indicate which row of tablets should be administered at each of the specified dosing times (8 AM, 1 PM, 6 PM, and 11 PM). Dose kits for subjects randomized to lofexidine 3.2 mg/day will contain full blister cards of active tablets. Dose kits for subjects randomized to lofexidine 2.4 mg/day will contain blister cards in which each dose row contains 3 active tablets and 1 placebo tablet. Dose kits for subjects randomized to placebo will contain full blister cards of placebo tablets.

For the Open-Label, Continuation Treatment part of the study (Days 8-14), subjects will receive lofexidine at variable dose, as determined by the Site Investigator (see [Section 13.2](#)).

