#### **14.3.3 Days 1-7 (Randomized, Double-Blind, Placebo-Controlled Treatment)**

After randomization, subjects will receive their first dose of study medication (lofexidine or placebo) during the 8 AM dosing window on Day 1. Subjects will be dosed 4 times daily from Day 1 through Day 7 at 8 AM, 1 PM, 6 PM, and 11 PM. Vital signs will be recorded within 30 minutes before every dose and 3.5 hours after the 8 AM, 1 PM, and 6 PM dose. Other clinical assessments will be gathered between 11:00 AM and noon each day. These clinical assessments are described in detail in [Sections 15.4](#) and [15.5](#).

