**17.3.1 Assessment of Effectiveness**

Summary statistics will be provided by treatment day (overall and by gender) for:

- SOWS-Gossop;
- OOWS-Handelsman;
- MCGI (Subject and Rater);
- VAS-E; and
- COWS.

In addition, the following will be summarized overall and by gender over Days 8-14:

- Duration of exposure;
- Number and proportion of subjects successfully completing detoxification as assessed by the Site Investigator;
- Distribution of number of days required to complete detoxification as assessed by the Site Investigator;
- Average daily dose of lofexidine; and
- Concomitant medications.

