6.5 Data Summaries

The data will be summarized in tabular form by treatment group (2.4 mg Lofexidine, 3.2 mg Lofexidine and Placebo) and overall. In addition safety data will be summarized by treatment

Effective: 14-Feb-13

Page 7 of 26

group where the 2.4 mg Lofexidine and 3.2 mg Lofexidine doses are combined to form a single Lofexidine treatment group.

For physical examination, when calculating the percentage reporting each category, the "Not Done" category will not be included in the denominator.

Subject demographics and baseline characteristics will be presented for the mITT population.

All safety data and protocol deviations will be presented for the safety population.

Subject disposition will be summarized using the enrolled population.

All efficacy variables will be assessed using the modified ITT population.

Graphical presentations of the data will also be provided where appropriate.

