6.13 Safety analysis

All subjects who receive at least dose one of study medication will be included in the analysis of safety.

Safety measures will be summarized for the following subject cohorts for the open label phase:

- All treated subjects;
- Treated subjects without urinary evidence of illicit drug use; and
- Treated subjects with urinary evidence of illicit drug use (may be further subdivided by type of illicit drug used).

Safety measures will only be summarized for all treated subjects for the double blind phase.

Extent of exposure

Extent of exposure will be described by whether the subject took the trial medication and the number of days exposure to double-blind study medication (last date of double-blind medication minus first date of double-blind medication + 1). Average daily dose of double-blind study medication will also be calculated. Exposure to open-label medication will also be calculated as last date of open-label medication - first date of open-label medication + 1. No allowance will be made for breaks in therapy in the exposure calculations. Average daily dose of open-label study medication will also be calculated. If the date of last dosing is completely missing for the trial medication then the date of last dosing will be taken for analysis purposes

Effective: 14-Feb-13

Page 18 of 26

as the date the medication was last dispensed. If only the month of the last dose is recorded, the first day of the month will be assumed as the last dosing date.

Adverse Events During the Double-Blind Phase of the Study

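### The SAP defines double-blind average daily dose as doses per day, which reads 4.0 in every arm at full adherence and carries no mg information

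*SAP*

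**What the plan says.** SAP section 6.13 (Extent of exposure) sets double-blind exposure in days as "last date of double-blind medication minus first date of double-blind medication + 1" and says that an average daily dose will also be calculated, without saying how. Addendum 1, Change 14 supplies the rule for the double-blind phase: the average is calculated "by number of doses/exposure (days"). The reason given is to make the definitions clearer. The same section keeps the rule that "No allowance will be made for breaks in therapy in the exposure calculations". Addendum 2 does not touch this text, so the Addendum 1 rule is the operative one.

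The protocol fixes the regimen for Days 1-7. Section 10.1 gives the arms as "lofexidine 2.4 mg total daily dose (0.6 mg QID), lofexidine 3.2 mg total daily dose (0.8 mg QID), or matching placebo". Section 14.3.3 states: "Subjects will be dosed 4 times daily from Day 1 through Day 7 at 8 AM, 1 PM, 6 PM, and 11 PM". Section 13.1 adds that "all subjects will receive a total of 16 tablets per day whether active, placebo, or in combination to achieve the assigned dose".

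For safety data, SAP section 6.5 requires an extra column in which the "2.4 mg Lofexidine and 3.2 mg Lofexidine doses are combined to form a single Lofexidine treatment group". SAP section 5.1 requires the mean, SD, minimum, quartiles and maximum for continuous variables.

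**The concern.** A variable named average daily dose should report an amount of drug per day. This one counts dosing occasions. The number of occasions is the same by design in every arm, and the only thing that differs between arms, the mg per occasion, is left out. A fully dosed placebo subject gets the same average daily dose as a fully dosed subject on 3.2 mg.

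The primary objective includes dose-response, and the two doses are to be compared descriptively for safety. Delivered exposure in mg/day is the natural background to that comparison. The protocol itself describes the arms in mg per day (section 10.1) and defines overdose in mg per day (section 16.9).

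**Working it through.** **Inputs.** Four doses per day on Days 1-7 (Protocol 14.3.3). Tablets of 0.2 mg, with 3, 4 or 0 active tablets among the 4 in each dose (Protocol 13.1). Denominator: last date minus first date plus 1, breaks included (SAP 6.13 and Addendum 1, Change 14). Dose holds are allowed (Protocol 13.2.2). Before completer status, discontinuation follows more than 2 missed doses in 24 hours or more than 6 in total (Protocol 14.5.1). I assume that each recorded dose is a full row of four tablets.

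**1. The protocol's own figures reproduce.**
- 2.4 mg arm: 4 × (3 × 0.2) = 2.4 mg/day.
- 3.2 mg arm: 4 × (4 × 0.2) = 3.2 mg/day.
- Placebo: 0 mg/day.
- Tablets: 4 × 4 = 16 per day in every arm.

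**2. The SAP formula at full adherence.** Doses / days = 28 / 7 = 4.0 in all three arms. The true ratio of 3.2 / 2.4 = 1.33 becomes 4.0 / 4.0 = 1.00. Reading doses as tablets does not help: 112 / 7 = 16.0 in every arm.

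**3. The formula below full adherence.** Four is a ceiling.

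| Subject | Doses / days | SAP value | mg/day at 0.6 mg | mg/day at 0.8 mg |
|---|---|---|---|---|
| Full dosing | 28 / 7 | 4.00 | 2.40 | 3.20 |
| Completer, one dose on Day 7 | 25 / 7 | 3.57 | 2.14 | 2.86 |
| The same, with 6 earlier missed doses | 19 / 7 | 2.71 | 1.63 | 2.17 |

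Comparing rows shows the reversal. A subject with 25 doses at 0.8 mg scores 3.57, below the 4.0 of a fully dosed subject at 0.6 mg, yet received 2.86 against 2.40 mg/day.

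**4. Effect of dropout on an arm mean.** The documents give no dropout rate, so this is an assumed range. A subject who leaves on day d after k doses that day, with none missed before, scores (4(d − 1) + k)/d, which runs from 1.0 to 4.0. With k equally likely to be 1 to 4, the mean for day d is 4 − 1.5/d. Averaged evenly over Days 1-6 it is 4 − 1.5 × 2.45/6 = 3.39. With everyone else at 4.0, the arm mean is 0.8 × 4 + 0.2 × 3.39 = 3.88 at 20% dropout and 0.2 × 4 + 0.8 × 3.39 = 3.51 at 80%. Arms can therefore differ on this variable, but the difference reflects doses missed and timing of dropout, not mg.

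**5. The pooled lofexidine column.** With the planned 225 per active arm, all fully dosed, the column shows a mean of 4.0, an SD of 0 and every quartile at 4.0. In mg/day the mean is (225 × 2.4 + 225 × 3.2)/450 = 2.8. Every subject lies 0.4 from that mean, so the SD is about 0.4, with a lower quartile of 2.4 and an upper quartile of 3.2. No single multiplier takes the first set of statistics to the second.

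**The case against.** The strongest reply is that mg per dose is fixed within each double-blind arm, so anyone can multiply by 0.6 or 0.8. That is right for each arm's column. The pooled mean then follows as the weighted average of the two arm means, and the pooled SD could be rebuilt from the arm means, SDs and sizes. The pooled percentiles cannot be rebuilt that way, and the pooled column on its own converts to nothing.

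Second, doses per day is useful in its own right. For a drug with dose-hold rules, it shows how often doses were withheld or missed. That stands, and it is a reason to keep the figure under an accurate name. A reader might infer that the formula hides any difference between arms. It does not: what it omits is the mg difference, and the value of 4.0 holds only at full adherence.

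Third, arm columns are labelled by dose, so few readers would believe that the arms received equal mg, and no planned test uses this variable. Both points are fair, and they limit the severity.

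Fourth, units might be set in table shells that are not part of the available text. That is possible, but a shell cannot be presumed to override a formula that the addendum states outright.

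Finally, a reader might extend the criticism to Days 8-14, where Protocol 17.3.1 lists "Average daily dose of lofexidine". The text does not support that: the formula sits only in the double-blind sentence. The open-label sentence says that an average will be calculated and gives no formula, which is an omission of a different kind.

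**Conclusion.** The point holds for the double-blind phase. The written rule returns dosing frequency under the name of dose. At full adherence it gives 4.0 where the quantity named is 2.4, 3.2 or 0 mg/day. Below full adherence it can order subjects opposite to their mg/day exposure (3.57 against 4.0, when mg/day is 2.86 against 2.40). The pooled lofexidine column cannot be read in mg/day.

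Severity is low. This is a descriptive exposure summary; the primary and secondary tests, the testing sequence and the power figures do not use it. A reader might infer that the safety or dose-response conclusions are compromised. The documents do not support that, because safety is summarised by treatment group rather than by this variable.

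The figures rest on the fixed QID regimen and on each recorded dose being complete. The dropout range in step 4 is illustrative, and the conclusion does not depend on it.

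**What to change.** Replace the rule in Change 14 with: double-blind average daily dose (mg/day) = number of doses taken × mg per dose for the treatment received (0.6, 0.8 or 0), divided by exposure days. Using treatment received matches the SAP's Safety population. Derive it per subject, so that the pooled column is summarised directly in mg/day. Report number of doses divided by exposure days as a separate line, named doses per day, with the compliance tables.

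The cost is one sentence of SAP text and one multiplication. Protocol 13.2.1 already requires the date and time of each Days 1-7 dose on the eCRF, so no new data are needed.

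Treat open-label separately. Its average daily dose needs a formula, and because the regimen is not fixed there (Protocol 13.2.1), that formula has to rest on tablets taken. Check first that these are captured for analysis. Protocol 12.3 keeps tablets dispensed and returned in a site log, SAP 6.8 refers to pill counts, and Addendum 1 notes that open-label dosing dates are not on the eCRF.
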